**15.7 BIAS**

To minimize bias, an independent Data Safety Monitoring Board (DSMB) (see section 20.3) will be responsible for monitoring safety and performance aspects of the study. The DSMB consists out of an uneven number of experts in the field, enabling the assessment and conclusion with majority votes. If needed, the DSMB may invite ad hoc team members, such as statistical support. These ad-hoc members will refrain of voting. To review safety events happening in the study – for some events, the DSMB may be requesting additional information from the investigational site or the core lab to allow a comprehensive review. DSMB will be responsible of adjudicating the primary safety endpoint.

Secondly, to evaluate the Primary Performance Endpoint a binary classification of individual electrophysiological parameter measurements into 'RBC-positive' and 'RBC-negative' is performed by 2 SENSOME experts independently. In case of discrepancies, a 3rd expert will decide on the classification. This process cannot be performed by independent reviewers. Following SENSOME's internal procedure (SEN\_QAS\_SOP\_1010), experts involved in annotating data shall not inspect the incoming validation dataset before the development is declared finished (the prediction models being fixed). As dataset inspection is also routine to detect anomalies, another SENSOME expert not involved in the development could be designated in the transition period (when the development phase is not terminated but the development set is completed).

Thirdly, an expert in the field of histopathology from an independent Core Lab (Mayo Clinic) will perform the histopathological analysis of the clots. The core lab will be blinded for the results of the CSGS. Rules of operation and responsibilities are outlined in the Core Lab Instructions.

Fourthly, another independent core lab (UCLA) will check the images. The imaging Core Lab will be set-up by 2 experienced readers. Both will check independently the pre-procedural, procedural and post-procedural images. Both readers will assess the primary safety endpoint. In case of disagreement between the 2 readers, a decision will be made by consensus. Rules of operation and responsibilities are outlined in the Core Lab Instructions.

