## 1. Introduction

The purpose of this Statistical Analysis Plan (SAP) is to prospectively outline the types of analyses and presentations of the data that will form the basis for conclusions regarding this clinical investigation. The analyses defined in this plan should answer the safety and performance objectives outlined in the Clinical Investigation Plan (hereunder called CIP or protocol), and explain in detail how the data will be handled and analysed, adhering to commonly accepted standards and practices for biostatistical analysis in the medical device industry.

This document contains information to support the generation of a Clinical Study Report (CSR) for Clinical Investigation Plan SEN\_CLOTILD\_FIH\_1, including detailed descriptions of the statistical methods to be applied, as well as the analysis summary tables and figures and patient data listings intended to present the analysis results. The analyses described are based on the final CIP (version 6, 12 June 2023). The SAP will be finalized prior to database lock and describes the statistical analysis as it is foreseen when the study is being planned. If circumstances should arise during the study rendering this analysis inappropriate, or if improved methods of analysis should arise, updates to the analyses may be made. Any deviations from the SAP after database lock, reasons for such deviations and all alternative or additional statistical analyses that may be performed, will be described in a SAP Addendum.

The planned analyses identified in this SAP may be included in regulatory submissions, medical presentations and manuscripts. Exploratory analyses, not identified in this SAP, may be performed to support the clinical development program. Any post-hoc or unplanned analyses that are performed but not identified in this SAP will be clearly identified in the CSR.

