The single electrode pair measurement is defined as the response to an applied micro-current through an electrode pair. Such a response is referred to as 'the electrophysiological parameter': it depends on the arrangement and type of cells and interspersed biochemical components. The response across a single electrode pair is composed of a set of real numbers (up to 32 for CSGS) which are not independent; this set of numbers is referred to as a 'spectrum' since it forms the response as the micro-current frequency is swept across a pre-defined range. This is also referred to as a 'local-scale measurement'. A measurement triggered by the Cloviz software collects at a given time point the spectrums from a pre-defined set of electrode pairs. This is also referred to as a 'sensor-scale measurement' since it sweeps the electrode pairs of the sensor.

The CSGS will be inserted and up to 6 measurements will be done: 1 measurement distal to the access catheter in circulating blood (this is the reference measurement), 1 measurement proximal to the site of occlusion, 2 to 3 measurements inside the occlusion and 1 measurement at the most distal advancement of the guidewire (ideally distal to the occlusion). The collection of measurements made in contact with the clot is referred to as the 'clot-scale' measurement.

[figure not shown]

Figure 1: Schematic view of the sensor presenting the different scales of measurements.

Data from the CSGS is synced to the cloud database. These data are processed offline. Individual electrophysiological measurements are annotated manually by Sensome experts by inspecting the signal and the histological content from the full clot.

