## 7. Bias

Since this is a single-arm study, no randomization is performed. Investigator, nor patients are blinded for the treatment.

To minimize bias, an independent Data Safety Monitoring Board (DSMB), also known as a Data Monitoring Committee (DMC), will be responsible for monitoring safety and performance aspects of the study. Rules of operation and responsibilities will be outlined in the DSMB Charter.

The DSMB consist out of an uneven number of experts in the field, enabling the assessment and conclusion with majority votes. If needed, the DSMB may invite ad hoc team members, such as statistical support. These ad-hoc members will refrain of voting. To review safety events happening in the study – for some events, the DSMB may be requesting additional information from the investigational site or the Core Lab to allow a comprehensive review. DSMB will be responsible of adjudicating the primary safety endpoint.

Secondly, to evaluate the Primary Performance Endpoint a binary classification of individual electrophysiological parameter measurements into 'RBC-positive' and 'RBC-negative' is performed by 2 Sensome experts independently. In case of discrepancies, a third expert will decide on the classification. This process cannot be performed by independent reviewers. Experts involved in annotating the development set shall not inspect the incoming validation dataset before the development is declared finished (the prediction models being fixed). As dataset inspection is also routine to detect anomalies, another Sensome expert not involved in the development could be designated in the transition period (when the development phase is not terminated but the development set is completed).

Thirdly, an expert in the field of histopathology from an independent Core Lab (Mayo Clinic) will perform the histopathological analysis of the clots. The Core Lab will be blinded for the results of the CSGS. Rules of operation and responsibilities are outlined in the Core Lab Instructions.

Fourthly, another independent imaging Core Lab (UCLA) will check the images. The imaging Core Lab will be set-up by 2 experienced readers. Both will check independently the pre-procedural, procedural and post-procedural images. Both readers will assess the primary safety endpoint. In case of disagreement between the 2 readers, a decision will be made by consensus. Rules of operation and responsibilities are outlined in the Core Lab Instructions.

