### **Validation dataset**

After completion of the development phase, data of the following interventions will be used in the validation dataset. The validation dataset shall be used to assess the generalization performance of the model(s) developed during the development phase. When moving to the validation stage, all steps used from input data, i.e. individual impedance spectrums for each electrode pair, to the score prediction shall be fully determined. When moving to the validation phase the model(s) shall be locked, remaining unchanged during the course of the validation phase.

This same procedure of splitting the dataset into two sets (development dataset and validation dataset) will be performed for the primary performance endpoint assessment as well as for the secondary and tertiary endpoint assessments.

Confidence intervals will be computed with the bootstrap.

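### SAP 1 leaves analysis details revisable until database lock, although the documents do not stop validation data being labelled and scored once the models are fixed

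*SAP*

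**What the plan says.** SAP section 1 sets the freezing point: "The SAP will be finalized prior to database lock". Until then, "if improved methods of analysis should arise, updates to the analyses may be made". The addendum is reserved for what comes later: "Any deviations from the SAP after database lock, reasons for such deviations", together with alternative or additional analyses. Analyses not identified in the SAP must be flagged in the study report.

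On the data, SAP 4 b) says: "Data from the CSGS is synced to the cloud database. These data are processed offline". The spectra are "annotated manually by Sensome experts by inspecting the signal and the histological content from the full clot".

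On access, Protocol 15.7 says that "experts involved in annotating data shall not inspect the incoming validation dataset before the development is declared finished". SAP 7 is narrower: "Experts involved in annotating the development set shall not inspect the incoming validation dataset before the development is declared finished". Both allow another sponsor expert, not involved in development, to be designated to check incoming data for anomalies during the transition period.

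On the model, SAP 8 c) i says: "When moving to the validation phase the model(s) shall be locked, remaining unchanged during the course of the validation phase". The sentence before it requires every step from the individual spectrum to the predicted score to be fully determined on entering validation.

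On timing, SAP 8 c) vii limits the interim analyses to safety and plans the final analysis of all endpoints after database lock.

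**The concern.** Finalising a SAP before database lock protects a trial whose results stay hidden until lock. Here the reference labels for the primary performance endpoint are set by the sponsor's own experts. Once the models are fixed, nothing in either document stops those experts from labelling the validation spectra, or stops the locked model from scoring them, while the database is still open. A method changed in that interval simply becomes the SAP. It is then neither a deviation after lock nor an analysis missing from the SAP, so neither disclosure rule in SAP 1 reaches it.

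Protocol 15.3 and SAP 8 c) i both say that the split into development and validation data removes optimistic bias. For that to hold, the whole analysis must be fixed before validation data are labelled or scored, not only the prediction model.

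**Working it through.** **1. What is frozen, and when**

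| Element | Where stated | Position |
|---|---|---|
| Prediction model; steps from spectrum to score | SAP 8 c) i | Fixed on entering validation |
| AUC as metric, on validation data only | Protocol 15.4.1 | A change needs an amendment with justification (Protocol 16.2) |
| Populations; list of anomaly criteria | Protocol 15.2, 15.6 | A change there needs an amendment |
| Endpoint analysis | SAP 8 c) vii | Scheduled after database lock; no rule on access |
| Inspection of validation data by annotators | Protocol 15.7, SAP 7 | Barred only until the models are fixed |
| Remaining SAP detail | SAP 1 | Revisable until database lock |

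**2. What stays open at SAP level**

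- *Bootstrap resampling unit.* SAP 8 c) i names the bootstrap but not whether measurements, acquisitions or patients are resampled. This affects the interval, not the AUC itself.
- *Exclusion for scatter in the reference measurement.* Protocol 15.6 and SAP 8 c) vi both give it without a numerical limit. If a limit is coded into the locked steps, it is fixed at model lock; the text does not say so.
- *Validation population.* Protocol 15.2 asks for a non-anomalous acquisition during a tagged measurement with clot contact. SAP 8 b) asks for data from at least one tag in the clot as judged by expert labelling, so the labels help decide who is analysed.
- *Secondary endpoint 2.* Protocol 15.4.2 admits interventions with at most one missing or anomalous individual measurement in the two tagged acquisitions. SAP 4 c) has no such filter.

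**3. The plan's own figures**

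Inputs (Protocol 15.5, SAP 6): A = 0.85; 3 clot-contact acquisitions per intervention; 5.44 measurements per acquisition; 53% positive and 47% negative.

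Hanley–McNeil: SE² = [A(1−A) + (n₊−1)(a−A²) + (n₋−1)(b−A²)] / (n₊n₋), with a = A/(2−A) = 0.7391 and b = 2A²/(1+A) = 0.7811.

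- 14 interventions: n = 14 × 3 × 5.44 = 228.5, so n₊ = 121.1 and n₋ = 107.4. SE = 0.02535 and width = 2 × 1.96 × 0.02535 = 0.0994.
- 13 interventions: n = 212.2 and width = 0.1031.

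So 14 is the smallest number that meets a width of 0.10. The total is (11 + 14)/0.60 = 41.67, rounded up to 42. Both figures reproduce.

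**4. Scale of the open choices (assumed inputs, not in the documents)**

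- *Interval.* With 3 × 5.44 = 16.32 measurements per intervention, the design effect is 1 + 15.32 × ICC. At an ICC of 0.1 it is 2.532, SE is 0.0403 and width is 2 × 1.96 × 0.0403 = 0.158. At 0.3 it is 5.596, SE is 0.0600 and width is 0.235. Resampling patients rather than measurements could therefore matter a good deal.
- *Point estimate.* Suppose the best of k analysis variants were chosen with the results known, using SE = 0.02535 and equal correlation between variants. By simulation, the mean gain runs from 0.003 (k = 2, correlation 0.95) to 0.021 (k = 5, correlation 0.5). The chance that the lower 95% limit lies above the true AUC rises from 2.5% to between 3.2% and 9.2%.

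**5. Timing**

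The 40% anomaly rate comes from the first 31 treated subjects (Protocol 15.6). If it applies per patient, 31 × 0.60 = 18.6 interventions were evaluable, which is 18.6 − 11 = 7.6 more than development needs. About 7 to 8 interventions beyond the development set may thus have existed before SAP version 2 (13/11/2023). The documents do not say whether anyone had inspected them.

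**The case against.** The plan has more protection than SAP 1 alone suggests. The locked steps run from raw spectrum to score. The metric, populations and anomaly list stand in the protocol, and Protocol 16.2 requires amendments to be justified and notified to, or approved by, the ethics committee and authorities. SAP versions are dated in a change history. Labelling under the SAP also uses histology, which is entered in the eCRF (SAP 8 a)), and Protocol 16.3 transfers the study database to the sponsor only after lock. The performance analysis is descriptive, with no pass mark to cross.

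Most of this stands, and it rules out several stronger readings. A reader might infer that the metric, exclusions and populations can be swapped without disclosure; the protocol prevents that for what it specifies. A reader might infer that the data sit in a system the sponsor owns; the SAP names no owner, and sponsor access is inferred from its experts annotating and inspecting the data. A reader might infer that the validation AUC has been or will be seen early; nothing shows this. The 53% positive share comes from the first 9 procedural successes, fewer than the 11 development interventions, so it does not show that validation data were labelled.

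What the objection does not remove is the gap itself. SAP 8 c) vii is a schedule, not a restriction on access. The histology route is not a firm barrier either: Protocol 15.6 already reports that 30 clots from the first 31 treated subjects were collected and analysed, so some core-laboratory information reaches the sponsor before lock.

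**Conclusion.** The point holds as a statement of what the plan permits. SAP 1 allows SAP-level methods to change between model lock and database lock, a period in which validation data can be labelled and scored, without recording the change as a deviation. The exposure is limited to the four items listed in the working; of these, only the scatter exclusion and the labelling-dependent population could move the primary AUC itself.

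The size of any bias cannot be derived from the documents. The gains of 0.003 to 0.021 in AUC rest on assumed numbers of variants and correlations, and on independent measurements; the wider intervals rest on assumed within-patient correlation. They show scale and predict nothing. There is no numerical error in the plan on this point. This is a cheap improvement that would support the plan's own claim to be free of optimistic bias.

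**What to change.** In SAP 1, replace the database-lock trigger with:

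> The SAP is final no later than model lock and before any validation acquisition is labelled or scored. Any later change, before or after database lock, is recorded with its date and reason, and the result under the previously specified method is also reported.

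The frozen text should settle the four open items: the resampling unit, a numerical limit for the scatter exclusion, one validation population and one filter for secondary endpoint 2, with protocol and SAP reconciled on the last two. If validation data had already been inspected when SAP version 2 was issued, state the date and what had been seen.

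The cost is wording. The validation set stays at 14 and the total at 42. The sponsor gives up the freedom to revise SAP-level methods between model lock and database lock without recording it as a deviation.

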## 2. Study objective

The objective of the study is to evaluate the safety and the possibility of Clotild® Smart Guidewire System (CSGS) to provide electrophysiological measurements. The electrophysiological measurements will be used to update CSGS's database and thus improve the prediction accuracy of the model in providing physicians with insights for mechanical thrombectomy.

The **primary objective** of the study is to evaluate the **safety** of using Clotild® Smart Guidewire System (CSGS) at the occlusion location during an EndoVascular Thrombectomy (EVT) procedure for the treatment of subjects with acute ischemic stroke eligible for EVT.

Safety will be evaluated by means of the amount of intracranial vessel perforations and/or dissections with the CSGS during the procedure.

The **secondary objective** of the study is to evaluate the **performance** of CSGS, defined here as the feasibility to measure electrophysiological properties of the occlusion in vivo during EVT procedures for the treatment of acute ischemic stroke.

Performance will be evaluated by the ability to correctly binary classify the clot as Red Blood Cell (RBC) positive or RBC negative, platelet positive or negative and fibrin positive or negative. Performance endpoints that focus on clot characterization are split in two categories: one category that demonstrates the ability of an automatic system to correctly identify the local composition of a clot

(local-scale), and the other category that reveals the extent of concordance between a number of local scale measurements made from the CSGS and the histological characterization by the Core Laboratory (Core Lab) of the full clot retrieved during the EVT procedure (clot scale).

The **tertiary objective** of the study is to explore possible relationships between CSGS measurements and intervention parameters such as first pass effect, number of passes to successfully retrieve the clot and other key parameters. Due to the nature of the tertiary objectives, not all centers may contribute to the data collection.

### 3. Study design and plan

This study is a prospective multi-centre, single-arm study to evaluate the safety and the performance of Clotild® Smart Guidewire System during endovascular thrombectomy (EVT) procedures, in subjects presenting acute ischemic stroke. The study will be performed in Australia and Europe.

Since this is a single-arm study, no control treatment is determined and no randomisation will occur. Subjects and investigators are not blinded for the treatment. Study data are captured until 24 hours (range 16-36 hrs) after the procedure. Assessment of the safety endpoint will be performed by an independent core imaging laboratory. Evaluation of the performance endpoints will be done by comparison of the predictions made by phenomenological modelling techniques with expert annotations of the sensor measurements and the histological evaluations by an independent core histology laboratory.

An overview of all follow-up times and respective captured information can be consulted in **table 1**.

The objectives and endpoints will be based on the data collected during the procedure and short follow-up period. There is a primary safety endpoint and a primary performance endpoint. There are 7 secondary endpoints and 6 tertiary endpoints that will be evaluated.

**Table 1. Study activity overview**

Parameter/Examination	Screening/Baseline	EVT procedure	24H (range 16- 36 hrs.) Post-procedure
Inclusion/Exclusion criteria	X		
Demographics & Medical History incl. Time of stroke onset, NIHSS, GCS	X		
Pregnancy test**	X		
Vital Signs (inc. ECG at screening)	X	X	
Laboratory assessments	X		
Patient Information/ informed consent	X		

Neuro Imaging exams	CT/CTA / MRI/MRA	DSA CT/CTA/MRI/MRA*	CT/CTA/MRI/MRA***
Timings (imaging, tPA, arterial puncture, recanalization)		X	
Thrombus collection		X	
AE/SAE		X	X
Concomitant medication, incl. Anti-thrombotic treatments	X	X	X

\* if available per local hospital practice

\*\* according to site specific standard of care (e.g. test, verbal communication)

\*\*\* CT/CTA / MRI/MRA if available per local hospital practice (range 2hrs - 36hs post procedure)

## 4. Endpoints

### a) Primary Safety Endpoint

The Primary Safety Endpoint is defined as the proportion of patients having intracranial vessel perforation and / or dissection due to CSGS usage at the site of usage in intracranial vessels by assessment by Interventional Neuroradiologist during the procedure and final adjudication of the DSA (Angiogram) by the Data Safety Monitoring Board.

The Interventional Neuroradiologist will complete if a vessel perforation/dissection due to CSGS usage at the site of usage occurred in the eCRF. The imaging Core Lab will assess the procedural images and will independently assess if a vessel perforation/dissection due to CSGS usage at the site of usage occurred. If one of both (investigator or Core Lab) suspects a vessel perforation/dissection, the DSMB will adjudicate if or not a vessel perforation/dissection occurred.

The proportion will be determined by

$$\frac{\text{number of patients with perforation or dissection}}{\text{number of patients in which the guidewire went through the sheath}}$$

Furthermore, a 95% confidence interval will be estimated.

